4.0 Enrollment/Randomization

Potential participants will be recruited via listserv email to undergraduate students in the School of Public Health-Bloomington, and interested participants will contact (phone or email) and meet with the investigator to discuss the project and ask questions. The informed consent and Concussion History & Health History Questionnaire will be given to the potential candidates. Participants who meet the inclusion criteria and are free of exclusionary factors will advance to the testing procedures.

We will use simple randomization method for group assignments. Upon inclusion of the participants, based on dice roll they will be randomly assigned into one of three groups: Heading group (number of dice 1 or 2), kicking group (number of dice 3 or 4), or standing group (number of dice 5 or 6). After assigned to groups, based on flipping a two-sided coin, participants will be further assigned into either TMS (head) or EEG (tail) experiments.

[name] (PI) will only know subjects' group assignment and ensure blinded experiment and data processing. [name] will randomly assign participants into three groups and perform soccer heading/kicking/standing protocol, and draw blood. Ocular-motor testing and data processing will be performed by [name] and blood biomarker experiments will be performed by [name]. The EEG experiment will be conducted by [name] and analyzed by [name]. The TMS experiment will be performed by [name] and analyzed by [name]. As noted, statistical analyses of all the data will be performed by [name]. These process will ensure single blind method.

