5.0 Study Procedures

Research Design

We will use a repeated measures design. The independent variable will be time (pre-test, 0h post-test, 2h post-test, 24h post-test). Control groups (kicking and standing) will be used to analyze any effects from bodily damage, exercise, and normal changes in dependent variables over time. The dependent variables assessed over time will include symptom scores, ocular-motor function, blood biomarker concentration, brain waves, and cortical excitability. Impact kinematics will also be assessed during soccer heading.

The study consists of 4 data collection time points in 2-day period. The 1st collection - pre-heading baseline-, followed by soccer heading intervention. The 2nd collection, 0h-post-heading time point (immediately after headings). The 3rd collection, 2h-post-heading time point (2h after headings). The 4th collection, 24h-post-heading time point (2nd day). This study design will enable to test outcome measures over 3 acute phases (Figure 5). The 1st day will last 4.5 hours and 2nd day will last 1.5 hours. Since we propose to include a total of 60 subjects in the study, we estimate data collection and primary analysis of 60 subjects will last approximately 15 months.

In order to address the potential residual effects of previous soccer-related injury or head trauma, we will recruit additional 20 age- and gender-matched healthy-non-athletic controls, against subjects in the soccer heading group to validate whether baseline values of each parameter are comparable to a healthy non-athletic cohort. However, regardless of whether there will be a difference in baseline between soccer players and healthy-controls, the purpose of the current study is to determine acute subconcussive head impact effects in the athletic population. Thus, the changes between soccer players and healthy controls will not terminate the study.

Soccer Heading Protocol

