The subject will then perform eye-movement task using the EYE-SYNC headset. This visual-tracking protocol has been replicated and validated in a number of concussion and sleep deprivation studies,⁴²⁻⁴⁷ however to our knowledge this study for the first time will unravel subconcussive effects. Prior to testing, a Snellen chart will be used to verify that the subject has a normal or corrected-to-normal vision (minimum 20/30). The subject will be seated in a normally lit room and stabilize the headset with two hands while the elbows placed on the desk. The visual stimulus will be presented using a 120-Hz frame rate LCD screen in the headset and binocular eye movements will be tracked by a single camera secured in the headset. The test stimulus consists of a red circular target, 0.5° diameter in a visual angle with a 0.2° black dot in the center. The target moves in a circular clockwise trajectory of 10° radius at 0.4 Hz, with the target speed corresponding to 25°/s. The entire testing sequence will last approximately 3 mins consisted of a calibration and 2 consecutive test runs. Calibration of the eye position is conducted by having the subject fixate on a target presented at eight locations on the circular path of the test stimulus and one additional fixation point at the center of the circular path. The fixation target was presented at these nine locations in a randomized order. Each of the two test runs consists of 6 cycles of circular movement corresponding to 15 s in duration per test run. The subject will be instructed as "follow the movement of the target as closely as possible."

Transcranial Magnetic Stimulation Assessment

After eye movement tasks, a subset of subjects (n=10) per group will participate in a transcranial magnetic stimulation (TMS) experiment, while the different subset of subjects (n=10) per group will participate in an electroencephalography experiment. These pilot studies are to assess subconcussive effects on neural activities. TMS will be used to assess physiological change in the primary motor cortex after subconcussive impacts. TMS works by electromagnetic induction: a current passed briefly through a coil of wire held over the scalp induces a magnetic field around the coil which, in turn, induces an electrical current in the underlying nerve cells on the surface of the brain. We will place electrodes in the hand to assess the cortical representation of an index finger muscle, first dorsal interosseous (FDI).

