There is minimal risk associated with TMS. In particular, we are using magnetic brain stimulation due to it being well-tolerated, versus direct electrical stimulation of the brain, which is very painful. TMS briefly activates nerve cells in a small area on the surface of the brain. The stimulator device uses the principle of 'electromagnetic induction' to produce a weak electric current on the surface of the brain. While the physical risk is almost none (assuming they have completed the TMS Checklist), there is the potential for the subject to have an adverse psychological reaction to the stimulation techniques. The possible side effects as it has been mentioned in literature are: seizure induction (rare), syncope (epiphenomenon), transient headache, transient neck pain, transient toothache, transient paresthesia, and transient hearing changes. Based on safety literatures on paired-pulse, there is no extra risk in paired pulse comparing to the single pulse. There is no reason to believe that single pulse TMS, itself, poses any hazard. Extensive use in [name] previous laboratory at Johns Hopkins School of Medicine has not resulted in any difficulties with the device that could pose a hazard to participants. TMS does not appear to pose any hazard to the brain beyond that of electric stimulation, which has been in clinical use for decades. The procedure appears to be safe and without any side effects. Some of the original subjects have been stimulated many

thousands of times. Some people may experience a mild headache from the stimulation. A headache, if it occurs, is usually mild and only lasts a few minutes beyond the end of the test. However, participants with a history of a migraine or other types of severe or frequent headaches will be excluded from the experiment.

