Our primary interest is to identify the changes in biomarker expression, ocular-motor, and neural function after subconcussive head impacts in the heading group; hence, each parameter at post-heading time points (0h, 2h, and 24h) will be compared with pre-heading baseline. Each time point of the control groups (kicking and standing) will aid to interpret whether or not changes in the heading group are due to subconcussive impact, exercise, bodily hit, or simply a daily variation. To this end, a series of mixed effects regression models (MRM) with random intercept will be used for all aims.⁴⁸ The first MRM will focus on the within-group pattern of changes in biomarker expressions (PINCH and Tau), ocular-motor performance (smooth pursuit velocity gain, phase error, and gaze position error), neural activity (delta, theta, alpha, and beta powers), and motor cortex excitability (I/O curve) in 3 groups across the duration of the study – 4 time points. Next MRM will focus on between-group analyses on the variables (heading, kicking, standing) against changes in the biomarker levels, ocular-motor function, and neural function. Predictor variables include time, group, and time by group interaction. All analyses will be conducted with SAS and significance will be set at $p < 0.05$.

Study Endpoint

Throughout the study, we set the study endpoint based on subjects' well-being measured via symptom checklist or verbal claim to researchers. Because the mild nature of head impact, we expect to observe a subtle change in our sensitive outcome variables after soccer headers. To date, there is virtually no scientific evidence available to set study endpoints using ocular-motor, blood biomarker, and neuronal activity, we will guide the study based on symptoms, meaning that if a subject experiences any concussion-related symptoms following blood draw, soccer heading, ocular-motor testing, EEG, and TMS, his or her participation will be terminated.

Symptom

When a subject experiences any symptoms related to concussion (headache, nausea, blurred vision, disorientation, fogginess, sensitivity to light and noise, etc.), his/her participation will be terminated. However, there has been no participant thus far reported concussion-related symptoms due to soccer heading, blood draw, nor ocular-motor performance.

Blood Biomarker

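### The pooled biomarker and eye-movement models leave out the randomised TMS/EEG split; adding it is a minor, inexpensive gain in precision and in protection against chance imbalance.

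*Protocol*

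**What the plan says.** Section 4.0 (Enrollment/Randomization) describes two successive simple randomisations. For the main comparison, "based on dice roll they will be randomly assigned into one of three groups". Then, "based on flipping a two-sided coin, participants will be further assigned into either TMS (head) or EEG (tail) experiments". No blocking, stratification or cap is stated for either step. Section 5.0 nevertheless gives a fixed split: "a subset of subjects (n=10) per group will participate in a transcranial magnetic stimulation (TMS) experiment", with another 10 per group going to EEG. Section 8.0 (Power analysis) repeats 10 per group for each technique.

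The Procedure Outline in section 5.0 puts symptoms, eye test and blood draw first in each session and TMS or EEG last. TMS takes 15-20 minutes and EEG 30-40 minutes, so sessions last about 40 minutes or about one hour. The 0h and 2h collections are both timed from the headings.

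Section 8.0 (Data analysis) applies random-intercept mixed models to all aims. The listed outcomes are PINCH and tau, three ocular-motor measures, EEG band powers and the I/O curve. On the right-hand side, "Predictor variables include time, group, and time by group interaction".

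**The concern.** The eye and blood outcomes of Aims 1 and 2 come from all subjects in an arm, both TMS and EEG halves. The pre-test TMS or EEG falls between the baseline and 0h measures, and the 0h test falls between the 0h and 2h measures. The two procedures are not alike. Section 6.0 lists, for TMS, "transient headache, transient neck pain, transient toothache, transient paresthesia, and transient hearing changes", while EEG is described as sitting still for longer. Any effect specific to one modality could therefore reach the next session's measures, and the gap between baseline and intervention depends on modality.

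Modality is a randomised, recorded design factor, and the stated predictors do not include it. Two things are at stake. One is precision: a modality effect on change from baseline goes into the residual. The other is chance imbalance: in the one trial that is run, arms may differ in their TMS share, and that fraction of any carry-over then sits in the time-by-group estimate.

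**Working it through.** **Inputs.** From section 8.0: effect 0.55, SD 0.6, power 0.80, 1.96 for alpha, 20 per group. From section 4.0: one fair coin flip per subject. From section 5.0: the session times. Assumption, not in the documents: the TMS-minus-EEG carry-over c on a change from baseline, taken as 0.1 to 0.55 on the scale where SD = 0.6. I also treat 0.6 as the SD of the change score.

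**1. The plan's own figure.** n = 2(1.96 + 0.8416)² × 0.6² / 0.55² = 18.68 per group, which reproduces. Power at 20 per group is Φ(0.55 / (0.6√(2/20)) − 1.96) = Φ(0.939) = 82.6%.

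**2. Can a coin give 10 and 10?**
- One arm of 20: C(20,10)/2²⁰ = 184,756/1,048,576 = 17.6%.
- All three arms: 0.176³ = about 0.5%.
- A split of 13/7 or worse: 26.3% in one arm; 1 − (1 − 0.263)³ = 60.0% in at least one of three.

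**3. Imbalance between two arms of 20.**
- SD of the difference in TMS share: √(2 × 0.25/20) = 0.158.
- Exact binomial: P(difference of at least 4 subjects) = 26.8%; P(at least 6) = 8.1%.
- The chance shift in a group contrast has SD 0.158c: 0.016 at c = 0.1, 0.047 at c = 0.3, 0.087 at c = 0.55.

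**4. Timing.** By session length, the EEG pre-test is about 60 − 40 = 20 minutes longer. From the step times the range is 30 − 20 = 10 to 40 − 15 = 25 minutes. This lengthens the baseline-to-intervention gap. It does not move the 0h and 2h points relative to heading.

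**5. Power without the term.** An unmodelled 50:50 factor raises the SD to √(0.36 + c²/4).

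| Assumed c | SD | Power at 20 per group | n needed per group |
|---|---|---|---|
| 0 (or term included) | 0.600 | 82.6% | 18.7 |
| 0.1 | 0.602 | 82.4% | 18.8 |
| 0.2 | 0.608 | 81.6% | 19.2 |
| 0.3 | 0.619 | 80.3% | 19.9 |
| 0.55 | 0.660 | 75.0% | 22.6 |

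**6. Bias and type I error.** A simulation (6,000 runs per setting, two arms of 20, change scores, coin-flip modality) gave mean estimates of about 0 when the truth was 0 and about 0.55 when it was 0.55, with or without the modality term. Type I error was 4.5-5.4% without it and 4.6-5.7% with it. Simulated power with and without the term was 79.2% and 80.1% at c = 0.1, 79.5% and 78.0% at c = 0.3, and 79.1% and 72.5% at c = 0.55. The term thus costs under one point when carry-over is negligible and gains several when it is large.

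**7. Within the heading group alone.** If TMS shifts the change by c and EEG by nothing, the average pre-to-post change moves by c/2. With 20 subjects, a nominal 5% test then rejects a true null about 6.6% of the time at c = 0.1, 19% at c = 0.3 and 46% at c = 0.55. A modality term does not remove this from the averaged time effect; the comparison with the control arms does, because they undergo the same tests.

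**The case against.** The strongest reply is that nothing is biased. The coin is independent of group, so leaving modality out keeps the time-by-group estimate unbiased, and its standard error already allows for chance imbalance. The simulation confirms this, and the point stands. A reader might infer that part of a TMS effect is systematically read as a heading effect; the design does not support that. Only precision and the imbalance of the realised draw are at issue.

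A reader might also extend the point to symptom scores. Section 5.0 names them as a dependent variable, but section 8.0 does not list them among the mixed-model outcomes, so the stated model cannot be faulted for them. EEG powers and the I/O curve each come from a single modality and are unaffected.

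Carry-over may be very small. Section 6.0 says a TMS headache, if it occurs, is usually mild and gone within minutes. Eye and blood measures precede TMS or EEG in each session, so only the next session can be touched. The shortest interval, from pre-test TMS to the 0h measures, contains the 10-minute intervention; the later intervals are much longer. The documents propose no route from TMS to PINCH, tau or pursuit. All this stands as a limit on size, although 'usually' does not exclude an effect at 0h.

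Finally, the wording of section 8.0 is not a closed list, and a SAP may add covariates. That is fair and lowers the weight of the point. It does not reconcile the fixed 10 and 10 in section 5.0 with the unrestricted coin in section 4.0. If the 10 and 10 were enforced, the imbalance figures would vanish, but no mechanism for this is given. Those figures also condition on arms of exactly 20, which the dice roll does not guarantee.

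**Conclusion.** The point holds as a minor one. The stated predictors for the pooled PINCH, tau and ocular-motor models omit a randomised factor that differs in procedure and by about 20 minutes per session, and the allocation method will almost never give the split that section 5.0 expects (about 0.5% for all three groups). The between-group contrast stays unbiased on average and type I error stays near 5%. The loss is in power: 82.6% falls to 82.4-80.3% for an assumed carry-over of 0.1 to 0.3, and to 75.0% only if carry-over is as large as the planned heading effect. These figures rest on c, which the documents do not give and which may be zero, on 0.6 being the SD of change, and on 20 subjects per arm. Neither systematic bias nor a defect in the symptom analysis is shown. Carry-over matters more for the pre-to-post comparison within the heading group, which section 8.0 calls the primary interest, because there it cannot be told apart from time.

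**What to change.** In section 8.0, add modality (TMS or EEG) and modality-by-time as fixed effects to the PINCH, tau and ocular-motor models. Report the realised TMS/EEG split in each arm, and reconcile the fixed 10 and 10 in section 5.0 with the coin flip in section 4.0. State that conclusions about heading rest on the time-by-group contrasts, because carry-over common to both modalities is removed only by comparison with the kicking and standing arms.

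The cost is one degree of freedom for modality and three for its interaction with the four time points, four in all. No new data are needed. If carry-over is negligible, the simulated power loss is under one percentage point.

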9.0 Privacy/Confidentiality Issues

All participant information, and even the fact that an individual is in the study, is considered confidential. Confidentiality will be assured in this study through several mechanisms. During interviews and treatments, the investigators and study coordinator will ensure physical privacy by conducting interviews in a closed room. Subjects will be assigned a subject number to help make data anonymous. The participant's Protected Health Information will be used for research purposes only. No names will accompany any data that is used for publication. To reduce the risk of confidentiality loss, electric data collected during the study will be stored on the university server and data collection sheets will be stored in a locked file cabinet in a locked room. The data will be stored indefinitely for data quality purpose for potential investigation after publishing the data. Only study personnel will have access to the data. All members of the research team are certified through the CITI program. Individual subject results will not be shared with the participants or their agents. Data analysis and publication will not include any identifying information.

Data Management

For symptoms, blood biomarker, and ocular-motor function, we will utilize spreadsheet to organize data and store in the IU Box account. Microsoft excel does not have range-checks system, however when we run statistical analysis using Statistical Analysis System (SAS), which can identify outlier and appropriate range for acquired data.

Symptom

Symptom scores will be manually transferred into an Excel spreadsheet for the future analyses. A tester or transferer will be blinded in regards to the group assignments and one's performance in other test parameters. The Excel spreadsheet will be saved in the university secured Box account, which will be backed up weekly.

Ocular-motor function

The eye-movement data acquired via the EYE-SYNC headset will be automatically saved in an Excel spreadsheet. The Excel spreadsheet will be saved in the university secured Box account, which will be backed up weekly.

Blood Biomarker

Biomarker expressions will be measured via Simoa HD-1 Analyzer and the data will be transferred into an Excel spreadsheet by the tester.

EEG

The EEG data will be processed offline using EEGLAB 5.03 software, which has a built-in range-check system. The data will be backed up weekly.

TMS

The TMS data will be captured and processed using Brainsight software (Rogue Research), where outliers can be identified by a built-in range-check system.

